In Part 1, provided that the dose on the preceding day is regarded safe and tolerable, the subsequent dose can be increased. The planned doses for the first 3 patients are 0.01 mg FE 204205 on Day 1, 0.025 mg FE 204205 on Day 2 and 0.05 mg FE 204205 on Day 3. After the SRC has evaluated the preliminary data on safety, tolerability and pharmacodynamics of FE 204205 from the first 3 patients, the planned doses for the remaining 3 subjects may be increased to maximum 0.025 mg FE 204205 on Day 1, 0.05 mg FE 204205 on Day 2 and 0.1 mg FE 204205 on Day 3 (see protocol section 3.4). Dose escalation in the subject on Days 2 and 3 will only commence provided that the increase in mean arterial pressure from baseline is  $< 15$  mmHg, absolute mean arterial pressure  $\leq 120$  mmHg, systolic blood pressure  $\leq 160$  mmHg, diastolic blood pressure  $\leq 100$  mmHg, and heart rate  $\geq 55$  beats per minute at all of the vital signs assessments during the 4 hours after start of infusion on the previous day. If these criteria are not met, the same dose will be administered the next day. If the increase of dose results in non-tolerable effects, the preceding tolerated dose will be reverted to for the remaining administration in that subject. The highest planned dose of 0.1 mg infused over 2 hours ( $= 0.05$  mg/hr) corresponds to the infusion rate applied for the dose level of 0.3 mg IV infused over 6 hours ( $= 0.05$  mg/hr) given to healthy subjects and is expected to not exceed the exposure in healthy subjects by means of  $C_{max}$  (expected  $C_{max}$ : approximately 3 ng/mL). At this dose level in healthy subjects (0.05 mg/hr IV over 6 hours), the mean arterial pressure increased (max. mean increase of +14 mmHg) and the pulse decreased. The dose level was safe and well tolerated in healthy subjects, as were dose levels up to 3 times higher (highest dose level studied in healthy subjects was 0.9 mg infused over 6 hours = 0.15 mg/hr).

The highest planned dose of 0.1 mg infused over 2 hours ( $= 0.05$  mg/hr) that may be reached on Day 3 is the same that was assigned to patient █ on Day 1. However, this dose level will only be reached in a patient in Part 1 who has already tolerated two lower dose levels of FE 204205 on Day 1 and Day 2 and met the dose escalation criteria above.

The chosen dose increments between dose levels (increasing by a factor of 2.5 from the starting dose, then maximum increase of factor 2 for the subsequent doses) are lower and thus more conservative than the ones used in the trials with healthy subjects, where a factor of  $\sim 3$  was applied for the respective dose range from 0.005 mg/hr to 0.05 mg/hr.

In Part 2 each patient will receive a 2-hour intravenous infusion of the dose of FE 204205 selected by the SRC, or placebo, on Day 1. The SRC will select the dose based on incidence and frequency of adverse events, safety laboratory data, ECG, systemic and portal haemodynamic parameters. The dose selected will be the maximum tolerated dose (MTD) or a lower dose. The MTD is defined as the dose level below the dose where one or more stopping criteria, as confirmed by a second measurement, are met in at least two subjects in Part 1.

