### **3.4 Safety Review Committee (SRC)**

An SRC, comprising at least one external expert in addition to the Principal Investigator and the Ferring representatives, will evaluate the safety, tolerability and pharmacodynamics of the compound.

Two scheduled meetings are planned: One SRC meeting will be held after the first 3 patients in Part 1 have completed all Visit 2 assessments, where the SRC will recommend whether the doses can be increased as planned or if a modified (lower) dose regimen should be applied. Another SRC meeting will be held after all subjects in Part 1 have completed all Visit 2 assessments in order to determine the dose that will be used in Part 2 of the trial. Furthermore, unscheduled meetings can be demanded anytime for any reasonable cause by the sponsor or the Investigator, e.g. due to any unforeseen adverse events. In such a situation, the SRC will recommend whether the dosing should continue according to the pre-defined dosing schedule, be changed to a different dosing schedule, or whether dosing should be stopped. A working procedure for the SRC will be described prior to study initiation.

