#### **4.5 Stopping Criteria**

The infusion will be interrupted and may be adjusted in the subject if any of the below stopping criteria occur, and halted for evaluation by the SRC when one or more criteria, as confirmed by a second measurement, are met in at least two subjects receiving the same treatment.

- Systolic blood pressure increased by 50% or more from the baseline and reaching >160 mmHg
- Systolic blood pressure 180 mmHg or higher
- Diastolic blood pressure 105 mmHg or higher
- Mean arterial pressure 130 mmHg or higher
- Heart rate 45 beats per minute or lower
- Signs or symptoms of mesenteric or peripheral ischemia, or hypertensive crises.

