## 5.5 Blinding / Unblinding

### 5.5.1 Blinding

Part 1 of the trial is open-labelled. In Part 2, all subjects, the Investigator, and all staff involved in the conduct of the trial will be blinded to the treatment received. The trial monitor will not be blinded, and no specific precautions will be taken to keep the pharmacist or personnel running the analyses of FE 204205 blinded.

It is the responsibility of the pharmacy to ensure that the syringes used for infusion in Part 2 are identical and non-distinguishable.

The pharmacy will receive the computer-generated randomisation list from Global Biometrics, Ferring Pharmaceuticals A/S.

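### In blinded Part 2 the two-subject safety halt is counted by treatment, and the supplied text gives that count to nobody who can see the treatment

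*Combined protocol and SAP*

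**What the plan says.** Section 4.5 has two levels. One subject who meets a stopping criterion has the infusion interrupted. Dosing is halted for SRC evaluation when criteria, "as confirmed by a second measurement, are met in at least two subjects receiving the same treatment".

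Section 5.5.1 states: "In Part 2, all subjects, the Investigator, and all staff involved in the conduct of the trial will be blinded to the treatment received". It adds: "The trial monitor will not be blinded, and no specific precautions will be taken to keep the pharmacist", and it sends the randomisation list to the pharmacy. Sections 3.5.3 and 5.5.2 allow emergency decoding, and optional unblinding of a patient who has been treated and whose data have been entered.

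Section 3.4 describes the committee's calendar: "Two scheduled meetings are planned: One SRC meeting will be held after the first 3 patients in Part 1". The second meeting follows the end of Part 1 and sets the Part 2 dose. Unscheduled meetings may be called by the sponsor or the Investigator. A working procedure for the SRC is promised but is not supplied.

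Section 3.5.4 notes that at 0.1 mg "this dose level will only be reached in a patient in Part 1 who has already tolerated two lower dose levels of FE 204205". For the second part, where the only dose is given on the first study day, it says: "In Part 2 each patient will receive a 2-hour intravenous infusion of the dose of FE 204205 selected by the SRC, or placebo". Section 3.1.2 plans 16 patients on active treatment and 4 on placebo.

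**The concern.** The halt was worded in a way that suits Part 1, which is open-label with every patient on FE 204205, so anyone at the site can see whether two patients share a treatment. In Part 2 the people who observe the stopping criteria do not know the allocation, and the people who know it are given no safety count to keep.

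The halt matters more in Part 2 because the within-patient escalation criteria and both scheduled SRC meetings belong to Part 1. If the trigger cannot be recognised, a cross-patient review depends on someone deciding to ask for one, or on decoding patients to find out whether the rule has been met.

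**Working it through.** The plan gives no event rate and no operating characteristics for the halt, so there is no figure of its own to reproduce here. Every event rate below is an assumption.

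**1. Who could apply the rule in Part 2**

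| Role | Sees the stopping criteria | Knows the allocation | Given the count in the supplied text |
|---|---|---|---|
| Investigator and site staff | yes | no (5.5.1) | no |
| Monitor | no such task stated | yes (5.5.1) | no |
| Pharmacist | no such task stated | holds the list (5.5.1) | no |
| SRC | when it meets (3.4) | not stated | no; working procedure not supplied |

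**2. What a blinded team can infer from two events.** Inputs: 16 active and 4 placebo (3.1.2). Suppose the events are unrelated to treatment.
- Both on active: (16 × 15)/(20 × 19) = 0.632
- One in each arm: (2 × 16 × 4)/(20 × 19) = 0.337
- Both on placebo: (4 × 3)/(20 × 19) = 0.032

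The halt would be due in the first and third cases and not in the second, so about a third of such pairs would not trigger it. A harmful drug would raise the first figure. Blinded staff still could not be sure in any given instance.

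**3. Whether the trigger is likely to be needed.** The chance that at least two of 16 active patients meet a criterion is 1 − (1 − p)^16 − 16p(1 − p)^15. For p = 10%, 20% and 30% this is 0.485, 0.859 and 0.974.

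**4. Cost of counting across both arms when the event rate is equal.**
- Same-treatment count, with allocation known: 1 − P(at most 1 of 16) × P(at most 1 of 4).
  - p = 2%: 1 − 0.9601 × 0.9977 = 0.042
  - p = 5%: 1 − 0.8108 × 0.9860 = 0.201
- Pooled count: 1 − P(at most 1 of 20).
  - p = 2%: 1 − 0.9401 = 0.060
  - p = 5%: 1 − 0.7358 = 0.264

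**5. Halts that involve a placebo patient.** Assume 5% on placebo, 10%, 20% or 30% on active, and a random dosing order. The first two events then include a placebo patient in about 12%, 10% and 7% of trials. With i active and j placebo events, the probability that the first two are not both active is 1 − [i(i − 1)]/[(i + j)(i + j − 1)]. This is averaged over the two binomial counts with i + j at least 2.

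**6. Speed.** In a simulation under the rates of step 5, the mean number of active patients dosed by the time of the halt (16 if it never occurs) was 12.4, 8.8 and 6.3 with the pooled count. With a same-treatment count and allocation known it was 12.9, 9.2 and 6.6.

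**The case against.** The case against is substantial.

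- **Missing text.** The SRC working procedure is a natural place to assign the count, so the gap is shown only for the supplied text.
- **Other protection.** Individual interruption under 4.5 needs no unblinding. Infusions may be paused or slowed (section 6). Vital signs are frequent (Table 6-2), and heart rate and oximetry are displayed continuously during the haemodynamic study (6.1). Serious events reach the sponsor within 24 hours (8.5.2). The Investigator or the sponsor may stop the study for safety (4.4), and either may call the SRC (3.4).
- **Decoding is available** (3.5.3, 5.5.2).
- **Small gain in speed.** Against a same-treatment count that someone actually keeps, pooling spares only 0.3 to 0.5 active patients (step 6).

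This lowers the priority and limits the claim. It does not remove the gap. These protections act within one patient or depend on someone's initiative, and none tells anyone that the two-subject condition has been met. Decoding patients to find out spends the blind on a question that wording can settle. The comparison in step 6 assumes a same-treatment count is running, which is what the supplied text does not provide.

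A reader might infer something stronger: that Part 2 exposes 16 patients unsafely to 0.05 or 0.1 mg without the Part 1 gates, and that a third scheduled SRC meeting is therefore required. The documents do not support that. The SRC may choose a dose below the maximum tolerated dose (3.5.4). Healthy subjects tolerated up to three times the highest planned infusion rate. The escalation gates (a rise in mean arterial pressure of 15 mmHg or more, or heart rate below 55) are far milder than the stopping limits (mean arterial pressure of 130 mmHg or higher, heart rate of 45 or lower), and nothing links missing a gate to meeting a stopping limit. Nor is it established that Part 2 would be the first untitrated exposure in patients: 3.5.4 mentions a patient assigned 0.1 mg on Day 1. An extra scheduled meeting is an optional design choice.

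**Conclusion.** The point holds as a gap in how one safety rule operates. In Part 2 the only automatic cross-patient halt depends on knowing the treatment, those who see the criteria are blinded, and the supplied text assigns the count to no unblinded role. Two events unrelated to treatment would fall in different arms 34% of the time, so blinded staff cannot read the rule from the events alone.

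The conclusion rests on the supplied text. If the SRC working procedure names an unblinded person to keep the count, only a cross-reference in 4.5 is missing. It does not mean that Part 2 patients are unprotected, and it calls no dose, gate or threshold into question. Priority is low to moderate, and the correction is cheap.

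**What to change.** Add one sentence to section 4.5: *In Part 2 the two subjects are counted across both arms, without unblinding.* Confirmation by a second measurement and all thresholds stay as they are. Site staff can then recognise the trigger themselves, and the decoding provisions in 5.5.2 are unchanged.

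The cost is a somewhat higher chance of a pause for SRC evaluation (step 4) and some halts that involve a placebo patient (step 5). No extra patients, procedures or decoding are needed. The alternative is to keep the same-treatment wording and name an unblinded person to maintain the count. That avoids the extra halts but needs a defined role and a route to the SRC that does not reveal allocation to the site.

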### **3.5.5 Selection and Timing of Dose for Each Subject**

The administration of the investigational medicinal product (IMP) will commence in the morning during fasting conditions.

### **3.5.6 Selection of the Trial Population**

Subjects with cirrhotic portal hypertension and anticipated HVPG  $\geq 12$  mmHg, are chosen as trial population since this is the target population. Measures will be taken to reach a balanced ratio between genders (i.e. at least 1/4 of each gender) in the trial.

### **3.5.7 Withdrawal Criteria**

The subject should be withdrawn if any signs of serious, or unexpected and unacceptable treatment emergent AEs occur, and may be withdrawn if the inclusion or exclusion criteria are violated during the conduct of the study. The subjects have the right to withdraw at any time for any reason without justification. In addition, a number of stopping criteria are defined, related to cardiovascular parameters (see Section 4.5).

### **3.5.8 Follow-up Procedures**

After the end-of-trial, the subject is referred to standard treatment according to medical need under the responsibility of the treating physician.

## 4 SELECTION OF TRIAL POPULATION

### 4.1 Trial Population

Subjects, 18-65 years of age, with verified cirrhotic portal hypertension and anticipated HVPG  $\geq 12$  mmHg.

#### 4.1.1 Inclusion Criteria

1. Signed written informed consent
2. Male or female patient, 18-65 years of age with confirmed evidence of cirrhosis
3. From medical history anticipated HVPG  $\geq 12$  mmHg
4. Negative pregnancy test at Screening and on Day -1
5. Agrees to use an adequate method of contraception during the study until the follow-up visit, if not abstinent. Adequate methods of contraception include condom with or without spermicidal gel (adequate only for male participants), intrauterine device, surgical sterilisation, vasectomy, oral contraceptive pill associated with inhibition of ovulation, depot progesterone injections
6. Negative urine drug screen and alcohol urine test at Screening and on Day -1

#### 4.1.2 Exclusion Criteria

1. Patients with co-existing disease including but not restricted to significant organ failure, decompensated cirrhosis with a Child Pugh score  $>12$  or requirement for organ support, and acute pancreatitis
2. Type 1 hepatorenal syndrome
3. Severe hyponatremia (serum sodium concentration  $<125$  mEq/L)
4. Acute-on-chronic liver failure
5. Hepatic encephalopathy  $\geq$ grade 2
6. Hepatocellular carcinoma outside the Milan criteria ( $<5$  cm for a single lesion or less than 3 lesions with the largest measuring  $\leq 3$  cm)
7. Bacterial infection within 7 days prior to dosing
8. Gastrointestinal bleeding within 6 weeks prior to dosing.
9. Severe renal impairment i.e. estimated creatinine clearance  $< 30$  mL/min calculated according to the Modification of Diet in Renal Disease (MDRD) study equation
10. History of underlying chronic heart disease, including but not restricted to heart failure NYHA class III or IV, angina pectoris, or myocardial infarction
11. Diagnosed ongoing hypertension
12. Symptomatic peripheral vascular disease including Raynaud's syndrome
13. Diagnosed chronic obstructive pulmonary disease (COPD)
14. Severe grade 3 anemia, i.e. Hb  $< 8.0$  g/dL ( $< 4.9$  mmol/L)

15. Use of vasopressin or terlipressin within 7 days prior to dosing
16. Permanent use of beta-blocker or a long-acting so called nitro-dilator, or if temporary use within 7 days prior to dosing
17. Use of treatments for hepatitis B or C virus within 6 months of randomisation or anticipated use during the trial period
18. Positive serology for human immunodeficiency virus (HIV)-1 or HIV-2
19. Women being pregnant or breastfeeding at screening and Day -1
20. Hypersensitivity towards any component of FE 204205 formulation
21. Sensitivity to contrast media
22. Intake of an investigational medicinal product within the last 8 weeks preceding screening or longer if judged by the investigator to possibly influence the outcome of the current study
23. Body mass index (BMI) <18 or >35 kg/m^2
24. Abuse of alcohol or drugs within 6 months prior to screening
25. Mental incapacity or language barrier precluding adequate understanding or co-operation
26. Previously included in this trial
27. Considered by the investigator to be unsuitable to participate in the study for any other reason

#### **4.2 Method of Assigning Subjects to Treatment Groups**

##### **4.2.1 Recruitment**

Patients with cirrhotic portal hypertension will be recruited among the patients enlisted for treatment at hospital clinics in the Barcelona area. However, all treatments will be conducted at the University of Barcelona, Hospital Clinic.

##### **4.2.2 Randomisation**

All subjects screened will be assigned a screening number. A subject number will be allotted to the subject according to a sequential subject number list in the order at which the subjects are found eligible. In Part 1, the subjects are not randomised. In Part 2, all subjects will be randomised to active treatment or placebo according to a computer-generated randomisation list provided by Global Biometrics, Ferring Pharmaceuticals A/S. Randomisation will be carried out on Day 1 before administration of IMP.

#### **4.3 Restrictions**

##### **4.3.1 Prior and Concomitant Therapies**

Concomitant medication with vasopressor substances, beta-blockers, or nitro-dilators is not allowed. Other concomitant medication may be administered at the discretion of the Investigator. Any concomitant medication will be recorded in the eCRF, together with the main reason for its prescription.

#### **4.3.2 Prohibited Therapy**

Treatment with vasoconstrictor substances (e.g. vasopressin, terlipressin, or catecholamines) or use of beta-blockers or a long-acting so called nitro-dilator, is not allowed.

#### **4.3.3 Other Restrictions**

Subjects should abstain from drinking alcoholic beverages for 72 hours before the screening visit and all subsequent visits to the clinical investigation unit. In addition, subjects should abstain from beverages containing caffeine and alcoholic beverages during the residential stay in both trial parts.

Intake of products containing poppy seeds (e.g., poppy cake) should be avoided for a period of at least 7 days before screening and admission to the clinic in both trial parts in order to avoid analytical interference with the drug screen for opiates.

The subjects should abstain from strenuous physical activity that is not within the subject's normal weekly routine for 48 hours prior to screening and from 48 hours prior to admission until the last safety examination in both trial parts.

Subjects must not participate in another clinical trial during the course of the present trial.

#### **4.4 Withdrawal Criteria**

The Investigator has the right and obligation to withdraw a subject should any signs of serious, or unexpected and unacceptable treatment emergent AEs occur. Furthermore, a subject may be withdrawn from the study if the inclusion or exclusion criteria are violated during the conduct of the study.

Both the Investigator (with regard to his/her participation) and Ferring, reserves the right to discontinue the study at any time for safety reasons, such as signs of unacceptable adverse reactions, or mortality, or any other reasons jeopardising the justification of the study. Such a termination will be implemented in a time frame that is compatible with the subject's well-being. If the study is prematurely terminated or suspended, the investigator should promptly inform the subjects and assure appropriate follow-up and treatment if required. Ferring Pharmaceuticals A/S will notify the Regulatory Authorities of any plans to terminate the study, and the Investigator will notify the Independent Ethics Committee (IEC).

The subjects have the right to withdraw from the trial at any time for any reason, without the need to justify their decision. For any discontinuation, the Investigator will obtain all the required details and document the date of the premature termination and the main reason in the eCRF. If possible, follow-up assessments should be performed for subjects who are withdrawn after start of infusion.

#### **4.5 Stopping Criteria**

The infusion will be interrupted and may be adjusted in the subject if any of the below stopping criteria occur, and halted for evaluation by the SRC when one or more criteria, as confirmed by a second measurement, are met in at least two subjects receiving the same treatment.

- Systolic blood pressure increased by 50% or more from the baseline and reaching >160 mmHg
- Systolic blood pressure 180 mmHg or higher
- Diastolic blood pressure 105 mmHg or higher
- Mean arterial pressure 130 mmHg or higher
- Heart rate 45 beats per minute or lower
- Signs or symptoms of mesenteric or peripheral ischemia, or hypertensive crises.

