FE 204205 is a novel, selective vasopressin 1a receptor ( $V_{1A}$ ) partial agonist in clinical development intended for the treatment of complications to cirrhotic portal hypertension. In comparison to full  $V_{1A}$  receptor agonists, the  $V_{1A}$  partial agonist FE 204205 is expected to have a substantially improved therapeutic index due to a lower maximal effect and lower risk for excessive vasoconstriction. In animal studies FE 204205 shows only approximately half of the maximal vasoconstriction produced by full agonists without any concomitant signs of ischemia (i.e. no increased lactate levels), which is assumed to result in adequate clinical vasoconstriction concomitant with the required safety.

Results from two Phase I studies, in which healthy subjects received FE 204205 intravenously, indicate that the maximal effect on vasoconstriction, by means of blood pressure, is reached at a plasma concentration of approximately 1 ng/ml, achieved by an intravenous infusion of 0.1 mg over 6 hours. The effect of the  $V_{1A}$  partial agonist FE 204205 appears to be capped compared to a full  $V_{1A}$  agonist, since increasing the dose 9-fold (from 0.1 mg to 0.9 mg over 6 hours) did not result in greater pharmacodynamic effects. Administration of 0.9 mg over 6 hours was well tolerated with an adverse events (AEs) profile related to the pharmacological effects of a  $V_{1A}$  receptor agonist.

Subcutaneous administration of FE 204205 resulted in the generation of an active metabolite (M1), characterised as a  $V_{1A}$  full agonist, at equimolar concentrations to FE 204205. The subcutaneous administration caused more AEs and of higher intensity than intravenous administration, and the maximal tolerated subcutaneous dose of FE 204205 was defined as 0.1 mg. After intravenous administration the M1 metabolite was detected only at very low concentrations,  $\leq 2\%$  of the FE 204205 concentration, and is not expected to show any appreciable pharmacodynamic effects in this trial.

This is the first study with FE 204205 in patients with cirrhotic portal hypertension and the selected endpoints will focus on the evaluation of safety and tolerability of the treatment in general, the investigation of effects on portal and systemic haemodynamics, and the pharmacokinetics of FE 204205.

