**Table 6-2 Study Flow Chart, Part 2**

Assessment	Screening	Treatment Period			End of trial
Visit No.	Visit 1	Visit 2		Visit 3	
Procedures / Days	-21 to -1	Day -1	Day 1	Day 2	Days 5-12
Informed consent	X				
Inclusion and exclusion criteria	X	X			
Randomisation			X		
Demographics	X				
Physical examination	X				X
Medical history	X	X			
Clinical chemistry, haematology, urinalysis	X	X	X 	X 	X
Serology/virology	X				
Urine drug screen	X	X			
Alcohol urine test	X	X			
Pregnancy test (serum)	X	X			X
12-lead ECG	X	X	X 	X 	X
Vital signs (non-invasive)	X	X	X 	X 	X
Adverse events	X	X	X	X	X
Concomitant medication	X	X	X	X	X
Venous blood gas including lactate		X	X 		
Administration of IMP			X		
Blood samples for PK and metabolites			X 		
Blood samples for metabolite pattern			X 		
Hepatic vein and pulmonary artery catheterization			X 		
Blood biomarkers			X 		
Urine sampling for urinary output, urinary biomarkers and excretion of FE 204205 and metabolites			X 		
Body weight			X 	X 	

 Blood samples for safety laboratory evaluations will be collected 6 hours after start of infusion on Day 1, and in the morning on Day 2.

 ECG will be collected pre-dose and at 1, 2, 3, and 6 hours after the start of the infusion on Day 1, and in the morning on Day 2.

 Vital signs comprising systolic and diastolic arterial blood pressure (including calculation of mean arterial pressure) and pulse will be assessed pre-dose, every 5 min until 30 min after start of infusion, then every 10 min until 1 hour after start of infusion, then every 15 min until 2.5 hours after start of infusion and thereafter 3, 4, and 6 hours after start of infusion on Day 1, and in the morning on Day 2. Temperature only pre-dose and 6 hours after start of infusion on Day 1.

 Venous blood gas including lactate will be collected 3 hours after the start of the infusion on Day 1.

 Blood samples for measurement of plasma concentration of FE 204205 and metabolites will be collected pre-dose and at 0.5, 1, 2, 2.5, 3, 4 and 5 and after the start of the infusion on Day 1.

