### 7.1.5 Venous Blood Gases including Lactate

Samples for analysis of blood gases (O2 and CO2) and lactate will be collected on Day -1, 3 hours after start of infusion on Days 1-3 in Part 1, and on Day -1 and 3 hours after start of infusion on Day 1 in Part 2.

Additional samples may be collected at the discretion of the Investigator.

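### Sections 4.5 and 3.5.4 require a confirming second measurement for every stopping criterion, but define none for clinical signs or symptoms of ischaemia

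*Combined protocol and SAP*

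**What the plan says.** Section 4.5 sets two rules on one list of six criteria.

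- **Individual rule.** A patient's infusion is interrupted if any criterion occurs. No confirmation is asked for.
- **Group rule.** Dosing is halted for SRC evaluation "when one or more criteria, as confirmed by a second measurement, are met in at least two subjects receiving the same treatment".

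Five of the six criteria are blood pressure or heart rate limits. The sixth is "Signs or symptoms of mesenteric or peripheral ischemia, or hypertensive crises". Nothing in 4.5 exempts it from confirmation.

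Section 3.5.4 defines the MTD as the dose level below the one at which "one or more stopping criteria, as confirmed by a second measurement, are met in at least two subjects in Part 1". It then leaves room to go lower: "The dose selected will be the maximum tolerated dose (MTD) or a lower dose".

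On lactate, footnote 4 of Table 6-2 (Part 2) reads: "Venous blood gas including lactate will be collected 3 hours after the start of the infusion on Day 1". Section 7.1.5 adds: "Additional samples may be collected at the discretion of the Investigator".

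Section 3.4 schedules two SRC meetings, one after the first three patients of Part 1 and one at the end of Part 1. None is scheduled in Part 2.

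**The concern.** A confirming reading makes sense for blood pressure and heart rate, where a single value can be spurious and another follows within minutes. It does not fit abdominal pain or cold digits. Section 4.5 does not say what would confirm such a finding: a repeat examination, a lactate value or something else.

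The two rules can also pull against each other. The individual rule requires the infusion to be interrupted. If that relieves the symptom, the confirmation needed by the group rule may never be obtained, and two such patients could go uncounted.

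Ischaemia is central to this programme. The background sections name tissue hypoxia and ischaemia as the hazard of full V1A agonists, and section 8.3 lists peripheral ischaemia among the effects to be closely watched. This is also the first study of the compound in these patients.

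**Working it through.** **1. How each criterion could be confirmed under the schedule (Part 2).**

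- Blood pressure and pulse, Table 6-2 footnote 3 and section 7.1.2: 5, 10, 15, 20, 25 and 30 min (6 readings), then 40, 50 and 60 min (3), then 75, 90, 105 and 120 min (4). That is 6 + 3 + 4 = 13 readings during the 2-hour infusion. The shorter list in section 7.1.10 (0.25, 0.5, 1, 1.5 and 2 h) gives 5. On either list a second reading is routine.
- Ischaemia: no scheduled re-examination. The synopsis background and section 1.1 treat raised lactate as a sign of ischaemia, but only one post-dose sample is scheduled. It falls at 3 hours, one hour after the infusion ends. Further samples are optional.

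So the condition can be met by schedule for the five numerical criteria, and for the sixth only if someone decides to look again.

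**2. Which group-level safeguards apply where.**

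- Part 1: patients are dosed one at a time (3.1.2), and both scheduled SRC meetings fall here.
- Part 2: 16 active patients receive one dose, with no scheduled SRC meeting. Besides the two-subject rule there are unscheduled SRC meetings (3.4) and discontinuation of the study (4.4). Both are discretionary.

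**3. Illustration of size.** The plan states no operating characteristic for this rule, so there is no figure to reproduce. Two quantities are assumed because the documents give neither:

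- *p*, the chance per active patient of an ischaemic sign or symptom without a confirmed blood pressure or heart rate breach;
- *c*, the share of such events that would be accepted as confirmed.

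Patients are taken as independent, and n = 16 comes from section 9.1. Then

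P(at least two cases) = 1 − (1 − p)^16 − 16p(1 − p)^15.

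At p = 2%: 1 − 0.7238 − 0.2363 = 0.040. At p = 10%: 1 − 0.1853 − 0.3294 = 0.485.

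Replacing p by pc gives the chance that the rule as written fires on these events. The difference is the chance of a missed halt.

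| p | At least two cases (missed halt if c = 0) | Rule fires if c = 0.5 | Missed halt if c = 0.5 |
|---|---|---|---|
| 2% | 0.040 | 0.011 | 0.029 |
| 5% | 0.189 | 0.059 | 0.130 |
| 10% | 0.485 | 0.189 | 0.296 |
| 20% | 0.859 | 0.485 | 0.374 |

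If every event is accepted (c = 1), nothing is missed. The second column is therefore an upper bound, at each assumed p, on halts missed when ischaemic cases alone should have triggered them. It leaves out the mixed pair of one confirmed vital-sign breach and one uncounted ischaemic case.

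In Part 1 at most six patients share a dose (0.025 mg or 0.05 mg, Table 5-1). The same formula with n = 6 gives 0.006, 0.033, 0.114 and 0.345 for at least two cases.

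**The case against.** The strongest reply is that a second measurement can only apply to something that is measured. On that ordinary reading the ischaemia item already counts on occurrence and there is no gap. This is probably the intent, but the text does not say so, and a halting rule should not depend on a generous reading.

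The second reply is that the practical protection is good, and this largely stands. All dosing is at one site. The investigator sits on the SRC, and either the investigator or the sponsor can call an extra meeting at any time (3.4). Both hold a power of termination: each "reserves the right to discontinue the study at any time for safety reasons, such as signs of unacceptable adverse reactions". Serious events reach the sponsor within 24 hours (8.5.2). A second ischaemic case would be seen by the team that can convene the SRC. Because the amended rule would still rest on the investigator's judgement, the gain over these routes is modest.

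Third, the group rule is not self-executing in Part 2. It counts subjects on the same treatment, while section 5.5.1 blinds the investigator and trial staff. Changing the confirmation clause does not resolve that.

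The documents do not support three stronger inferences that a reader might draw:

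- **That a patient with ischaemia would go on being infused.** Individual interruption needs no confirmation, and section 4.4 obliges the investigator to withdraw a subject with signs of serious adverse events.
- **That patients dosed after a second case are avoidable exposures.** This would assume that no event is ever confirmed, that nobody uses the discretionary routes, and that a halt ends dosing. The halt is for evaluation, and after an unscheduled review the SRC may recommend continuing (3.4).
- **That a hypertensive crisis should also be exempt.** It is defined largely by blood pressure, which Table 6-2 re-reads every 5 to 15 minutes during the infusion, so its pressure component can be confirmed.

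**Conclusion.** The wording defect is real and its practical effect is limited. Sections 4.5 and 3.5.4 apply a confirmation condition to a clinical criterion for which no second measurement is defined. Followed literally, a transient ischaemic event need not count toward the two-subject halt or the MTD.

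It matters most in Part 2, where no SRC meeting is scheduled. For the MTD the effect is small, because the SRC weighs adverse events and may select a lower dose.

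The effect cannot be quantified from the documents. The 4% (p = 2%) and 49% (p = 10%) figures rest on assumed rates and on no event being confirmed. The low end may be nearer the truth: section 3.5.4 reports that infusion rates up to three times the highest planned here were well tolerated, although in healthy subjects.

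One reservation remains. The SRC working procedure mentioned in 3.4 is a separate document that is not available here and may already settle the point. The change is worth making, with medium confidence.

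**What to change.** In section 4.5, limit second-measurement confirmation to the five blood pressure and heart rate criteria and to the blood pressure component of a hypertensive crisis. State that mesenteric or peripheral ischaemia, as judged by the investigator, counts toward the two-subject halt when it occurs. Use the same wording in the MTD definition in 3.5.4. If the SRC working procedure already says this, carry it into the protocol.

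The cost is one sentence and one matching edit, with no new data, samples or patients. The downside is an occasional extra SRC review prompted by a non-specific symptom.
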